### **7.1.1 Molecular pre-screening**

Not applicable.

### **7.1.2 Screening**

After signing the study ICF, the screening assessments will be done within 1 to 28 days prior to randomization or within 1 to 14 days prior to randomization for selected assessments (see [Table 7-1a](#) for list of assessments to be performed).

**Note:** Any screening assessment that is done outside the screening window (Day -28 to Day -1 or Day -14 to Day -1 as applicable) must be repeated prior to randomization.

Re-screening of patients is only allowed once per patient if the patient was not registered as entering the treatment phase before (i.e. IRT randomization). In this case the Subject No assigned to the patient initially will be used and the patient will be identified with this number throughout her entire participation to the study.

For laboratory evaluations used to determine eligibility, a repeated evaluation within the screening window is permitted for screening results out of the defined range before screen failing the patient. If the repeated laboratory result meets the criteria, that result may be used to determine eligibility. If the repeated laboratory result does not meet the criteria, the patient will be considered a screening failure. In case rescreening occurs, all evaluations re-assessed should meet the eligibility criteria. A new informed consent form must be signed only if there is an interruption in the patient's eligibility evaluation and the investigator chooses to re-screen the patient following screen failure; the 28 day screen period does not apply to the informed consent process. If a new informed consent form is signed, adverse events and medical history will be assessed relative to the new informed consent date.

Assessments of patient reported outcomes should be collected prior to any clinical assessments, drug dosing or diagnostic testing.

Any imaging assessments already completed during the regular work-up of the patient within 28 days prior to randomization, including before signing the main study ICF can be considered as the baseline images for this study.

#### **7.1.2.1 Eligibility screening**

Following registering in the IRT for screening, patient eligibility will be checked once all screening procedures are completed. The eligibility check will be embedded in the IRT system. Please refer and comply with detailed guidelines in the IRT manual.

#### **7.1.2.2 Information to be collected on screening failures**

Patients who sign an informed consent but fail to be started on treatment for any reason will be considered a screen failure. The reason for not being started on treatment will be entered on the Screening Phase Disposition Page. The demographic information, informed consent, and Inclusion/Exclusion pages must also be completed for Screen Failure patients. No other data will be entered into the clinical database for patients who are screen failures, unless the patient

experienced a Serious Adverse Event during the Screening Phase (see [Section 8](#) for SAE reporting details).

### 7.1.2.3 Patient demographics and other baseline characteristics

The data that will be collected on patient characteristics at screening includes:

- Demography (Date of birth and initials (where permitted), sex, race, ethnicity, source of patient referral)
- Diagnosis and extent of cancer (including staging at study entry and histology/cytology)
- Medical history (e.g., important medical, surgical, and allergic conditions from the patient's medical history which could have an impact on the patient's evaluation) / current medical conditions (e.g., all relevant current medical conditions which are present at the time of signing informed consent). Ongoing medical conditions, symptoms and disease which are recorded on the Medical History eCRF should include the toxicity grade.
- ER, PgR and HER2 status
- All prior antineoplastic therapies including surgical interventions and chemo-, biologic-, immunologic- and radiation-therapies provided as treatment for cancer prior to the administration of study drug.
- All medications and significant non-drug therapies taken within 30 days before the first dose is administered. They must be recorded on the Prior and Concomitant medication or Surgical and medical procedures eCRF page and updated on a continual basis if there are any new changes to the medications.
- Patient-reported outcome questionnaires (EORTC QLQ-C30, EORTC QLQ-BR23, EQ-5D-5L, [REDACTED]) (See [Section 7.2.6](#)).

Furthermore the following assessments will be performed:

- Vital signs
- Height, weight
- Physical examination
- Performance status (ECOG)
- Laboratory evaluations (hematology, , INR, chemistry, lipid panel, urinalysis)
- ECG
- ECHO/MUGA
- Radiological assessments (e.g. CT Scan)

### 7.1.3 Run-in period

Not applicable.

### 7.1.4 Treatment period

Patients will be treated with tamoxifen or a NSAI + goserelin + LEE011 **or** tamoxifen or a NSAI + goserelin + placebo until disease progression, unacceptable toxicity, withdrawal of consent by the patient, patient is lost to follow up, death, discontinuation from the study

treatment due to any other reason or the sponsor terminates the study. For details of assessments, refer to [Table 7-1a](#).

### **7.1.5 End of treatment visit including study completion and study treatment discontinuation**

Patients who completely discontinue study treatment should be scheduled for an End of Treatment (EOT) visit within 15 days following the date study treatment is permanently discontinued, at which time all of the assessments listed for the EOT visit will be performed. For details of assessments, refer to [Table 7-1a](#). If the decision to discontinue the patient occurs at a regularly scheduled visit, that visit may become the EOT visit rather than having the patient return for an additional visit.

An End of phase disposition eCRF page should be completed, giving the date and reason for stopping the study treatment. If a withdrawal occurs, or if the patient fails to return for visits, the investigator must determine the primary reason for a patient's premature withdrawal from the study and record this information on the EOT eCRF page. The EOT visit is not considered the end of the study.

At a minimum, all patients who discontinue study treatment, including those who refuse to return for a final visit, will be contacted for safety evaluations during the 30 days following the last dose of study treatment.

If a patient discontinues study treatment, but continues study assessments, the patient remains on study until such time as she completes protocol criteria for ending study assessments. At that time, the reason for study completion should be recorded on the End of Post Treatment Phase Disposition CRF page.

The Investigator must contact the IRT to register the subject's discontinuation.

#### **7.1.5.1 Discontinuation of study treatment**

Patients **may** voluntarily discontinue from the study treatment for any reason at any time.

If a patient decides to discontinue from the study treatment, the investigator must make reasonable effort (e.g. telephone, e-mail, letter) to determine the primary reason for this decision and record this information in the patient's chart and on the appropriate CRF pages. They may be considered withdrawn if they state an intention to withdraw, fail to return for visits, or become lost to follow-up for any other reason.

The investigator should discontinue study treatment for a given patient if, he/she believes that continuation would be detrimental to the patient's well-being.

Patients may be withdrawn from the study treatment if any of the following occur:

- Adverse Event (including, but not limited to  $QTcF \geq 501$  msec, confirmed at repeated ECG measurements and recurrent after dose adjustment was performed; documented episode of ventricular tachycardia, or ventricular fibrillation)
- Lost to follow-up
- Physician decision
- Progressive Disease

- Protocol deviation
- Study terminated by sponsor
- Technical problems

Patients must be withdrawn from the study treatment if any of the following occur:

- Pregnancy
- Death
- Subject/Guardian decision

In addition to the general withdrawal criteria, the following study specific criteria will also require study treatment discontinuation:

- Adjustments to study treatment that result in discontinuation. Please refer to [Section 6.3](#).
- Use of prohibited medication. Please refer to [Section 6.4.3](#).

Patients who discontinue study treatment should NOT be considered withdrawn from the study. They should return for the assessments indicated in [Section 7.1](#). If they fail to return for these assessments for unknown reasons, reasonable effort (e.g. telephone, email, letter) should be made to contact them as specified in [Section 7.1.5](#).

Patients who discontinue study treatment should undergo an End of Treatment (EOT) visit followed by a 30 day safety follow-up.

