**Table 6-2 Dose modification guideline**

	LEE011/placebo	
	Dose	Number of capsules & strength
Starting dose	600 mg	3 x 200 mg capsules
First dose reduction	400 mg	2 x 200 mg capsules
Second dose reduction	200 mg	1 x 200 mg capsules

Recommendations for dose reduction, interruption or discontinuation of LEE011 in the management of adverse reactions are summarized in [Table 6-3](#), [Table 6-4](#), [Table 6-5](#), [Table 6-6](#) and [Table 6-7](#).

Clinical judgment of the treating physician should guide the management plan of each patient based on individual benefit/risk assessment. However, for events requiring a discontinuation in [Table 6-3](#), [Table 6-4](#), [Table 6-5](#), [Table 6-6](#) and [Table 6-7](#) or listed in [Section 7.1.5.1](#), treatment must be discontinued.

If a patient inadvertently doses on a rest day (e.g. days 22-28 of any given cycle), LEE011/placebo will be interrupted to ensure 7 consecutive rest days and avoid overdose. The visit schedule will not be adjusted.

For assessment of patients' eligibility to the study, only laboratory results from the central laboratory will be used.

**Table 6-3 LEE011/placebo dose adjustment and management recommendations for hematological adverse reactions (CTC AE v4.03)**

Toxicity	Grade	Dose Adjustment and Management Recommendations
Thrombocytopenia	1 ≥75 x 10  /L	No dose adjustment required.
	2 ≥50 x 10  /L – <75 x 10  /L	Dose interruption until recovery to grade ≤1. Re-initiate LEE011/placebo at the same dose.
	3 ≥25 x 10  /L - <50 x 10  /L	Dose interruption until recovery to grade ≤1.  Re-initiate LEE011/placebo at the same dose level. 
 
• If toxicity recurs at grade 3: temporary dose interruption until recovery to grade ≤1 and reduce LEE011/placebo to the next lower dose level.
 

	4 <25 x 10  /L	Dose interruption until recovery to grade ≤1. Re-initiate LEE011/placebo at the next lower dose level. 
 
• If toxicity recurs at grade 4: discontinue LEE011/placebo.
 

Absolute neutrophil count (ANC)	1 ≥1.5 x 10  /L	No dose adjustment required.
	2 ≥1.0 - <1.5 x 10  /L	No dose adjustment required.

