Grade 3* QTc ≥ 501 ms on at least two separate ECGs	
Interrupt LEE011/placebo. Perform steps 1-4 as directed in “For All Grades.”
 
Perform a repeat ECG within one hour of the first QTcF of ≥501 ms.
 
If QTcF remains ≥ 501 ms, consult with a cardiologist (or qualified specialist) and repeat cardiac monitoring as clinically indicated until the QTcF returns to < 481 ms.
 
 
• If QTcF returns to < 481 ms, LEE011/placebo will be reduced by 1 dose level. Refer to Table 6-2 for dosing schedule.
 
• If QTcF remains ≥ 481 ms after performing steps 1-4 as directed in “For All Grades,” discontinue LEE011/placebo.
 
 
Repeat ECGs 7 days and 14 days after dose resumption (then as clinically indicated) for any patients who had therapy interrupted due to QTcF ≥ 501 ms.
 
If QTcF of ≥ 501 ms recurs, discontinue LEE011/placebo.

Grade 4* [QT/QTc ≥ 501 or > 60 ms change from baseline] and [Torsades de pointes or polymorphic ventricular tachycardia, or signs/symptoms of serious arrhythmia]	
Discontinue LEE011/placebo. Perform steps 1-4 as directed in “For All Grades.”
 
 
• Obtain local cardiologist (or qualified specialist) consultation and repeat cardiac monitoring as indicated until the QTcF returns to <481 ms
 

*All values refer to the average of triplicate measurements	

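### Recurrent QTcF ≥501 ms and ventricular tachycardia or fibrillation fall under conflicting stopping rules in Protocol Sections 6.3.1.4 and 7.1.5.1 and Tables 6-5 and 6-7

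*Protocol*

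**What the plan says.** Protocol Section 7.1.5.1 holds three lists.

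- The first is permissive: "Patients may be withdrawn from the study treatment if any of the following occur". Its adverse-event entry names QTcF ≥501 ms, "confirmed at repeated ECG measurements and recurrent after dose adjustment was performed; documented episode of ventricular tachycardia, or ventricular fibrillation".
- The second is mandatory: "Patients must be withdrawn from the study treatment if any of the following occur". It holds only pregnancy, death and subject/guardian decision.
- The third gives study-specific criteria that also require study treatment to stop. One is "Adjustments to study treatment that result in discontinuation", with a reference to Section 6.3.

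Section 6.3.1.4, in the text below Table 6-2, first leaves management to clinical judgment. It then makes an exception: for events requiring discontinuation in Tables 6-3 to 6-7, or listed in Section 7.1.5.1, "treatment must be discontinued".

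Table 6-5 states in its grade 3 row: "If QTcF of ≥ 501 ms recurs, discontinue LEE011/placebo". Its grade 4 row stops LEE011/placebo when a QT criterion and a serious arrhythmia occur together. Section 6.3.1.8 sends all other adverse events to Table 6-7. There, a first grade 2 or 3 event leads to interruption and restart of LEE011/placebo, and a grade 4 event to its discontinuation.

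Section 6.1 defines study treatment as the triple combination. Section 6.1.4 lets a patient who stops LEE011/placebo for a reason other than progression continue tamoxifen or an NSAI.

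**The concern.** The permissive and mandatory lists stand next to each other in 7.1.5.1, so *may* there cannot be taken as loose drafting for *must*. Yet 6.3.1.4 cites the section as a whole and uses the citation to remove discretion. The same safety event therefore has more than one instruction, and two sites could act differently while both cite the protocol.

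The events are not incidental. The protocol counts QT prolongation among the important identified risks of ribociclib (Section 1.4.1.1). It also reports more significant QT events with tamoxifen plus LEE011 in this study's primary analysis (Section 6.1).

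The statistical consequence lies in reporting. The final-CSR SAP tabulates discontinuation of study treatment from the end-of-treatment page (Section 3.4). It tabulates partial discontinuation of ribociclib/placebo from the dosing record (Section 3.5.5), and protocol deviations by category (Section 3.2). Which table a patient enters after the same event, and whether a deviation is recorded, would depend on which passage the site followed.

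**Working it through.** The plan gives no figure on this point and no arithmetic applies. The check sets the current passages side by side.

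| Event | 7.1.5.1, first list | 6.3.1.4 | Section 6.3 tables | 7.1.5.1, third list |
|---|---|---|---|---|
| Confirmed QTcF ≥501 ms, recurring after dose adjustment | Optional | Mandatory | Table 6-5: stop LEE011/placebo | Required |
| Ventricular tachycardia or fibrillation that meets the Table 6-5 grade 4 criteria, or is grade 4 under Table 6-7 | Optional | Mandatory | Stop LEE011/placebo | Required |
| Ventricular tachycardia of grade 2 or 3, outside the Table 6-5 grade 4 criteria, first occurrence | Optional | Mandatory | Table 6-7: interrupt, then restart LEE011/placebo | Not triggered |

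**Row 1.** The event is optional in the first list. It is required through the third list, because Table 6-5 belongs to Section 6.3. Section 7.1.5.1 thus disagrees with itself, whatever 6.3.1.4 is taken to mean.

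**Row 2.** The tables stop LEE011/placebo and the third list makes that binding. The permissive entry "documented episode of ventricular tachycardia, or ventricular fibrillation" still says otherwise.

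**Row 3.** Three answers exist: optional, mandatory, and interrupt-and-restart.

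**What stops.**

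1. Tables 6-5 and 6-7 name LEE011/placebo.
2. Section 7.1.5.1 speaks of study treatment, which Section 6.1 defines as all three components.
3. Section 6.3.1.4 says only treatment.
4. Section 6.1.4 allows the endocrine partner to continue after LEE011/placebo stops, whereas the third list of 7.1.5.1 requires study treatment to stop.

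So the obligation and its scope are both unclear.

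**Effect on the primary analysis.** Section 3.8.1.1 of the primary-analysis SAP states that discontinuing study treatment is not a reason to censor PFS. The stopping rule does not enter the censoring rule, the alpha or the event count.

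**The case against.** The best defence reads the passages narrowly. The reference in 6.3.1.4 could mean only those events in 7.1.5.1 that require discontinuation, since that section has its own mandatory lists. The literal reading would compel withdrawal for any protocol deviation or technical problem, which few sites would accept. Scope could also reconcile the rest: LEE011/placebo must stop, while withdrawal from the whole combination remains optional.

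Part of this stands. On the narrow reading, row 3 reduces to an option to withdraw beside an instruction to interrupt and restart, and the two can coexist. But 6.3.1.4 does not state that limit. The scope argument also fails for recurrent QTcF ≥501 ms, because the third list of 7.1.5.1 requires study treatment, not LEE011/placebo alone, to stop.

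Four stronger readings are tempting, and the documents do not support them.

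- A reader might infer that no table covers ventricular tachycardia or fibrillation outside Table 6-5. Table 6-7 does, and it stops LEE011/placebo at grade 4. Section 8.1.1 equates life-threatening with grade 4 where CTCAE has no grading.
- A reader might add disease progression, which is also on the permissive list. Section 6.3.1.4 concerns adverse reactions, and Section 7.1.4 bounds treatment in its own terms: "placebo until disease progression, unacceptable toxicity, withdrawal of consent by the patient". Section 6.1.5 does the same, so these passages can be read together.
- A reader might infer a bias in OS or unrecorded exposure. The wording applies to both arms, which were blinded until Amendment 6. By then the OS objective had been met, and no further formal OS analysis is planned (Section 10.5.1). Adverse events are recorded for at least 30 days after the last dose (Section 8.1.1).
- A reader might apply the QT rates in the background section to a trial arm. The 3.3% in Section 1.4.1.1 is QTcF above 480 ms. The 5.4% in Section 1.2.1.3 is any QTcF of 500 ms or more at 600 mg as a single agent. Neither is a rate of confirmed recurrence after dose adjustment.

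**Conclusion.** The inconsistency is real and stands in current text. For recurrent QTcF ≥501 ms it holds on either reading of the cross-reference. For ventricular tachycardia of grade 2 or 3 outside the Table 6-5 grade 4 criteria, it depends on taking the reference in 6.3.1.4 at its word. For grade 4 arrhythmia, the tables settle that LEE011/placebo stops; the permissive wording and the question of which components stop remain open.

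The number of patients affected cannot be derived, because the documents give no frequency for confirmed recurrent QTcF ≥501 ms or for ventricular tachycardia or fibrillation. An upper limit on current exposure follows from Amendment 7: 79 ribociclib-arm patients on study treatment plus 8 placebo-arm patients who had crossed over gives 79 + 8 = 87. This assumes that all of them were still taking LEE011. It bounds the patients to whom the LEE011 rules could apply at that date; it does not predict events.

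The consequence is inconsistent safety conduct and ambiguous discontinuation and deviation summaries. The primary and key secondary inferences are not in question. No view is taken here on which clinical rule is right.

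**What to change.** Reconcile Section 6.3.1.4, Tables 6-5 and 6-7, and Section 7.1.5.1:

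1. Put recurrent QTcF ≥501 ms and ventricular tachycardia or fibrillation each under one rule only, by grade where the rule depends on grade. The sponsor decides which rule.
2. State for each rule whether it covers LEE011/placebo alone or the whole study treatment, consistently with Section 6.1.4.
3. Limit the cross-reference in 6.3.1.4 to the mandatory criteria of 7.1.5.1.

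The cost is protocol wording, the approvals that any amendment needs under Section 12.1, and a clarification to sites. No new procedure, data item or analysis is required.

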#### **7.1.5.2 Replacement policy**

Not applicable.

#### **7.1.6 Follow-up period**

##### **7.1.6.1 Safety follow-up**

All patients will be followed up for safety up to 30 days after last dose of study treatment (tamoxifen/NSAI + goserelin + LEE011/placebo). Patients whose treatment is interrupted or permanently discontinued due to an AE, including abnormal laboratory value, must be followed until resolution or stabilization of the event, whichever comes first. This could include all study assessments appropriate to monitor the event.

##### **7.1.6.2 Efficacy follow-up**

For patients who discontinue treatment for reasons other than disease progression, death, lost to follow-up, or withdrawal of consent, tumor assessments (see [Section 7.2.1](#)) and selected patient reported outcomes (see [Section 7.2.6](#)) must continue to be performed every 8 weeks during the first 18 months and every 12 weeks until 36 months, then change to as clinically indicated until disease progression, death, lost to follow-up, or withdrawal of consent. At that time, the reason for study completion should be recorded on the End of Post treatment phase Disposition eCRF page. If a patient starts a new anti-cancer therapy prior to progression, tumor evaluations should continue with the same above schedule ([Table 7-1a](#)) until disease progression is documented. In addition, all new anticancer therapies given after the last dose of

the study drug, until disease progression, death, lost to follow-up, or withdrawal of consent will be recorded in the eCRFs.

### **7.1.6.3 Survival follow-up**

All patients will be followed for survival status every 12 weeks (see [Section 4.1.5](#)) including documentation of the start of new antineoplastic therapy, until death, lost to follow-up, or withdrawal of consent. Additional survival assessments may be performed outside the 12 weeks follow up schedules if a survival update is required for an interim assessment to meet safety or regulatory needs.

Survival information can be obtained via phone, and information will be documented in the source documents and relevant eCRFs.

During the survival follow up, subsequent anti-neoplastic therapies initiated after study treatment discontinuation will be collected along with the start/end date and date of disease progression on subsequent therapies.

### **7.1.6.4 Lost to follow-up**

For patients whose status is unclear because they fail to appear for study visits without stating an intention to withdraw consent, the investigator should show "due diligence" by contacting the patient, family or family physician as agreed in the informed consent and by documenting in the source documents steps taken to contact the patient, e.g. dates of telephone calls, registered letters, etc. A patient should not be considered lost to follow-up until due diligence has been completed. Patients lost to follow-up should be recorded as such on the appropriate Disposition CRF.

